4.1.2.1.1. Multiple Imputation Based Tipping-Point Analysis

A multiple imputation-based tipping-point (MI-TP) analysis is planned as a sensitivity analysis to explore how different patterns of Lp(a) percent change post treatment discontinuation by different treatment groups could impact the treatment comparisons.

To start with, missing Lp(a) percent change from baseline data are imputed through multiple imputation using all non-missing data (excluding data collected after ICEs) from the same treatment group under the MAR assumption. A fixed percentage penalty is then added to these imputed values at the Week 12 visit before analysing treatment differences with the ANCOVA model. In the analysis, the magnitude of the penalties added for both treatment groups under comparison is varied, and the impact that these variations would have on the study conclusion is evaluated. A 2-dimentional space of penalties will be assessed for each dose of LY3473329 and placebo ranging from -30% to 30%. MI-TP aims to evaluate the robustness of the superiority claim to the assumptions of using the observed data to impute the missing Lp(a) level in all treatment groups.

4.1.2.2. Analysis method for treatment-regimen estimand

The primary endpoint will also be analyzed according to the treatment-regimen estimand, which represents the efficacy regardless of discontinuation of intervention or initiation of Lp(a) modifying medications. The assessment of efficacy measures guided by the treatment regimen estimand will be conducted using the FAS (Section 3), and an ANCOVA model will be used to analyze the measures as described in Section 4.1.2.1.

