Additionally, laboratory assessments at Visit 801 will provide information about the pharmacodynamic (PD) offset of study intervention on Lp(a).

	Period I - Pre- Screening	Period II - Screening		Period III - Treatment Period							Period IV - Post- Treatment Follow-Up	
Visit number	601	1	2	3	4	5	6	7	8	ED	801	
Weeks from randomization	≤6	≤3		1	2	4	8	12	12*	_	4 weeks from last dose	*Visit 8 occurs 1-3 days after final dose
Visit interval tolerance (days)	See Section 1.3	_	_	±2	±3	±3	±4	±4	_	_	±5	
Fasting Visit		X	X	X	X	X	X	X				If a participant arrives not fasted, schedule the laboratory draw for another date. See Section 5.3.1.
Pre-Screening informed consent	X											
Informed consent		X										The ICF must be signed before any protocol- specific tests or procedures are performed. See Appendix 10.1.3 for additional details.
Inclusion and exclusion criteria, review and confirm		X	X									Inclusion and exclusion criteria should be confirmed-prior to drug assignment and administration of first dose of study intervention.
Demographics		X										Includes year of birth, sex, ethnicity (where permissible), and race.
Preexisting conditions and medical history, including relevant surgical history		X										All conditions ongoing and relevant past surgical and medical history should be collected.
Prespecified medical history (indication and history of interest)		X										Prespecified medical history includes indication and history of cardiovascular events.
Prior treatments for indication		X										Relevant prior therapies include, but are not limited to, lipid lowering medications.
Substance use (alcohol, caffeine, and tobacco use)		X										
Concomitant medications		X	X	X	X	X	X	X		X	X	Additional data will be collected for medications of interest.

	Period I - Pre- Screening	Period II - Screening		Per	riod I	II - Ti	reatm	nent P	eriod		Period IV - Post- Treatment Follow-Up	
Visit number	601	1	2	3	4	5	6	7	8	ED	801	
Weeks from randomization	≤6	≤3		1	2	4	8	12	12*		4 weeks from last dose	*Visit 8 occurs 1-3 days after final dose
Visit interval tolerance (days)	See Section 1.3		_	±2	±3	±3	±4	±4	-	_	±5	
Fasting Visit		X	X	X	X	X	X	X				If a participant arrives not fasted, schedule the laboratory draw for another date. See Section 5.3.1.
AEs	X	X	X	X	X	X	X	X		X	X	Any events that occur after signing the informed consent are considered AEs as defined (Section 10.3). Additional data are collected for certain AEs.
Physical Evaluation												

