7.1. Discontinuation of Study Intervention

When necessary, a participant may be permanently discontinued from study intervention. If so, the participant will remain in the study to complete procedures for an ED visit and post-treatment follow-up, if applicable, as shown in the SoA.

A participant should be permanently discontinued from study intervention if

- the participant becomes pregnant during the study
- in the opinion of the investigator, the participant should permanently discontinue the study intervention for safety reasons
- if the investigator determines that a systemic hypersensitivity reaction has occurred related to study intervention administration, the participant may be permanently discontinued from the study intervention, and the sponsor's designated medical monitor should be notified. If the investigator is uncertain about whether a systemic hypersensitivity reaction has occurred and whether discontinuation of study intervention is warranted, the investigator may consult the sponsor
- the participant has an AE or an SAE or a clinically significant change in a laboratory value that, in the opinion of the investigator, merits discontinuation of study intervention and appropriate measures being taken
- if the participant experiences a hepatic event or liver test abnormality as specified in the liver chemistry stopping criteria (see Section 7.1.1), and
- HBV or HCV: The participant tests positive for HBV DNA (see Section 8.2.5) or tests positive for HCV RNA (Section 8.2.6).

Note: The HBV DNA result is to be confirmed if initial positive test result is positive but below the level of quantification. Prior to discontinuation of any immunomodulatory and/or immunosuppressive therapy, including study intervention, the participant is to be referred to, evaluated, and managed by a specialist physician with expertise in evaluation and management of viral hepatitis. The timing of discontinuation from study intervention relative to the initiation of any antiviral treatment for hepatitis is to be based on the recommendation of the consulting specialist physician, in conjunction with the investigator, and aligned with medical guidelines and standard of care.

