2.1. Multiplicity Adjustment

Treatment comparisons will be performed for the primary objective at the full significance level of 0.05. No multiplicity adjustments will be made for the analysis of secondary and exploratory objectives.

3. Analysis Sets

This table defines the analysis population and datasets for the purposes of analysis.

Population	Description
Screened	All participants who sign the ICF.
Randomized	All participants who are randomly assigned to a treatment arm.
Efficacy Analysis Set (EAS)	Data obtained during treatment period from all randomly assigned participants who are exposed to at least 1 dose of double-blind study treatment. Excludes data after discontinuation of study drug or initiation of Lp(a) modifying medication.
Full Analysis Set (FAS)	Data obtained during the treatment period from all randomly assigned participants who are exposed to at least 1 dose of intervention, regardless of adherence to intervention or initiation of Lp(a) modifying medication.
Safety Analysis Set (SS)	Data obtained during the treatment period plus safety follow-up from all randomly assigned participants who are exposed to at least 1 dose of intervention, regardless of adherence to intervention or initiation of Lp(a) modifying medication.

Abbreviation: ICF = informed consent form.

4. Statistical Analyses

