4.1.2. Analysis methods

4.1.2.1. Analysis method for efficacy estimand

Unless otherwise specified, the primary endpoint, secondary endpoints, and exploratory endpoints will be analyzed according to the efficacy estimand, which represents the efficacy had participants adhered to the randomized treatment without initiating Lp(a) modifying medications. Considered Lp(a) modifying medications are listed in Table EKBC.4.3. The assessment of efficacy measurements guided by the efficacy estimand will be conducted using the EAS (Section 3).

Table EKBC.4.3. Lp(a) Modifying Medica	tions
--	-------

Category	Medication
Lp(a)-Altering therapies	 statins PCSK9 inhibitors prescription-dose niacin mipomersen testosterone, estrogens, anti-estrogens, progestins, selective estrogen receptor modulators, or growth hormone
Excluded Treatment Medical Devices, and/or Procedures	 lipid apheresis any investigational drug, biological agent, or device other than study provided investigational product

A restricted maximum likelihood-based, mixed-effect model repeated measures (MMRM) analysis will be used to analyze continuous longitudinal endpoints. All the longitudinal observations at each scheduled postbaseline visit will be included in the analysis. The MMRM model will include the fixed class effects of treatment group (LY 10 mg, LY 60 mg, LY 240 mg, and placebo), strata (country and baseline Lp(a) stratum [<275 nmol/L, \geq 275 nmol/L as measured by the apo(a) assay]), visit, and treatment-by-visit interaction, as well as the continuous baseline value. An unstructured covariance structure will be used to model the within-participant errors. Significance tests will be based on LS means and Type III tests. If this analysis fails to converge, the following covariance structures will be tested in order:

- 1. Toeplitz with heterogeneity
- 2. autoregressive with heterogeneity
- 3. compound symmetry with heterogeneous variances
- 4. Toeplitz
- 5. autoregressive, and
- 6. compound symmetry without heterogeneous variances.

The first covariance structure that converges will be used. The Kenward-Roger approximation will be used to estimate denominator degrees of freedom.

If the data does not warrant the MMRM model, then an ANCOVA model with treatment group, strata, and the continuous baseline value will be used to analyze the continuous endpoint. Data for participants with missing values at Week 12 will be imputed using the multiple imputation

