method under the MAR assumption. Estimates and standard errors from multiple imputed datasets will be combined using Rubin's rules.

For binary endpoints derived from a continuous variable, the missing value in the underlying continuous variable will be imputed first based on the missing at random assumption (MAR), and then the corresponding binary variable will be derived.

A logistic regression model with treatment group and strata as fixed effects and the continuous baseline value as a covariate will be used to examine the treatment difference with missing endpoints imputed. The unconditional treatment group effect will be assessed by risk difference and relative risk using the marginal standardization method, where the treatment group-specific risk will be derived from the counterfactual risks for each participant that are predicted with the fitted logistic model (Ye et al. 2023). The estimated treatment group-specific risk, risk difference, relative risk, p-value and 95% CI will be presented.

For endpoints involving Lp(a), the Lp(a) strata class effects will be excluded from the above models.

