4.3.2. Main analytical approach

The analytical approaches are specified for the efficacy estimand in Section 4.1.2.1 (MMRM) and for the treatment regimen estimand in Section 4.1.2.2 (ANCOVA). The primary efficacy measure will be log-transformed prior to statistical analyses.

For each estimand, LY3473329 will be declared superior to placebo in controlling Lp(a) if the p-value is less than 0.05 for both the analysis conducted with the apo(a) assay data and the analysis conducted with the intact Lp(a) assay data.

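### For drug discontinuation, the treatment-regimen analysis fills in on-drug Week 12 Lp(a) values and so largely repeats the efficacy estimand

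*SAP*

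**What the plan says.** SAP Section 1.1 defines the treatment-regimen estimand as the Week 12 percent change irrespective of stopping drug or starting other Lp(a)-modifying medication, and justifies it as a picture of real-life use.

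SAP Section 4.1.2.2 gives the method in one sentence: the assessment under the "treatment regimen estimand will be conducted using the FAS (Section 3), and an ANCOVA model will be used to analyze the measures", with a pointer to Section 4.1.2.1. The ANCOVA paragraph there carries the missing-data rule: "Data for participants with missing values at Week 12 will be imputed using the multiple imputation", a sentence that continues "method under the MAR assumption. Estimates and standard errors from multiple imputed datasets will be combined using Rubin's rules". The SAP gives no other rule for this estimand.

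The data available to it are set in three places:

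- **FAS (SAP Section 3):** "Data obtained during the treatment period from all randomly assigned participants who are exposed to at least 1 dose of intervention", regardless of adherence. The Safety Analysis Set adds the follow-up period; the FAS does not.
- **After permanent discontinuation (Protocol 7.1):** "the participant will remain in the study to complete procedures for an ED visit and post-treatment follow-up, if applicable, as shown in the SoA".
- **Schedule (Protocol 1.3):** Lp(a) is drawn at Visits 3 to 7, at the ED visit, and at Visit 801 about 4 weeks after the last dose. The Visit 801 sample is there to show how Lp(a) recovers off drug.

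The Protocol Synopsis states that the Lp(a) effect disappears once drug is stopped. SAP 4.3.2 allows a superiority declaration under each of the two estimands.

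**The concern.** A treatment-regimen analysis needs either off-drug Week 12 measurements or an imputation that represents being off drug. This plan has almost none of the former and does not specify the latter. MAR imputation then borrows from participants in the same arm who are still taking drug, so someone who stopped at Week 2 receives a Week 12 value much like that of an adherent participant. That is the hypothetical question of the efficacy estimand, reported under a treatment-regimen label.

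At stake are the size and meaning of the secondary estimate. It would be presented as reflecting real-life behaviour, the bias favours LY3473329, and it does not shrink with sample size. The point is limited to drug discontinuation. For newly started Lp(a)-modifying medication the FAS keeps data that the EAS drops, so the two analyses can differ there.

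**Working it through.** **1. The plan's own figures.** SAP Section 5 gives 233 randomized 1:2:2:2, 10% dropout, SD 20, a 60% reduction and two-sided alpha of 0.05. Thirty plus three times 60 is 210 completers, and 210/0.9 = 233.3. The standard error is 20 × √(1/30 + 1/60) = 4.47 for 10 mg versus placebo and 20 × √(2/60) = 3.65 for the larger arms. A difference of 60 is 13.4 and 16.4 standard errors, so power above 99% is reproduced.

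**2. How many off-drug Week 12 values could exist.** Take the 10% dropout as a proxy for drug discontinuation: 0.10 × 233 = about 23 participants (3.3 on 10 mg, 6.7 in each other arm). If stops are spread evenly over 84 days (assumption), 4/84 = 5% to 8/84 = 10% of them fall in the last 4 to 8 days. That is 1 to 2 participants in the whole trial, still near on-drug levels. If every ED sample after Week 8 counted as Week 12, 28/84 = one third of stops would contribute, again mostly with near on-drug values.

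**3. Size of the gap.** The primary measure is log-transformed. Let d be the share of the drug arm off drug and r the off-drug ratio to baseline at Week 12. Placebo is assumed unchanged.

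- True treatment-regimen effect: exp[(1 − d) × ln 0.4 + d × ln r] − 1
- MAR target: 0.4 − 1 = −60%

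Example, d = 0.10 and r = 1: exp(0.9 × −0.9163) − 1 = exp(−0.8247) − 1 = −56.2%, a gap of 3.8 points.

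| Off drug (d) | Effect lost by Week 12 | True effect | Overstatement (points) |
|---|---|---|---|
| 3% | all (r = 1) | −58.9% | 1.1 |
| 5% | all | −58.1% | 1.9 |
| 10% | all | −56.2% | 3.8 |
| 15% | all | −54.1% | 5.9 |
| 5% | half (r = 0.7) | −58.9% | 1.1 |
| 10% | half | −57.7% | 2.3 |
| 15% | half | −56.5% | 3.5 |
| 10% | a quarter (r = 0.55) | −58.7% | 1.3 |

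On the untransformed percent scale the gap at 10% with full return is larger: 60 × 0.10 = 6.0 points (54.0 against 60).

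**4. Does MAR return the on-drug effect?** A simulation on the log scale used 67 per arm, 400 runs per setting, evenly spread stops, off-drug Lp(a) recovering at an assumed rate of 1 per week, and within-arm regression imputation from baseline and earlier on-drug visits. True effect against MAR estimate was 58.3 against 60.0 at 5% off drug, 56.3 against 59.9 at 10%, and 52.5 against 59.9 at 20%.

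**5. Scale and power.** With SD 20 and 60 per arm, the 95% CI half-width is 1.96 × 3.65 = 7.2 points. On the back-transformed scale with an assumed log SD of 0.3 to 0.5, it is 100 × 0.4 × 1.96 × SD × √(2/60) = 4.3 to 7.2 points. Power under the true regimen effect, in the worst arm at 10% with full return on the percent scale: mean −54, mixture SD √(400 + 0.09 × 3600) = 26.9, 33 against 67 participants, SE √(724/33 + 400/67) = 5.3, and 54/5.3 is about 10. Power stays above 99%.

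**The case against.** **The tipping-point analysis already covers this.** Its stated purpose in SAP 4.1.2.1.1 is to explore Lp(a) patterns after discontinuation. At its extreme corner (+30 drug, −30 placebo) it moves the contrast among missing participants by 60 points, or 6 points overall at 10% missing in both arms, which equals the full-return gap on the percent scale. That is a fair test of the superiority conclusion. However, half the shift comes from penalizing placebo. The drug-arm limit alone moves an imputed −60% only to −30%, giving 57.0 overall at 10% missing where full return gives 54.0. The analysis also sits under the efficacy estimand, imputes "using all non-missing data (excluding data collected after ICEs) from the same treatment group under the MAR assumption", and yields no treatment-regimen estimate.

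**Section 4.1.2.2 never mentions MAR.** True: the rule arrives by cross-reference, from a paragraph written for cases where the MMRM is not suitable. But no other rule is given, so following the plan leads to MAR.

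**The effect is small and secondary.** The efficacy estimand is primary, Protocol 9.3.2 makes the treatment-regimen comparison optional, and Protocol 7.2 expects discontinuation to be uncommon. This limits the severity. SAP 4.1.2.2 nonetheless commits to the analysis, and 4.3.2 attaches a superiority declaration to it.

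**Full return to baseline is an upper bound.** This stands. The documents give no time course for Lp(a) offset, and late stoppers will have recovered only partly. The half-lost and quarter-lost rows are there for that reason.

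**Reference-based imputation is also untestable.** It is, and it may be conservative for late stoppers. It still agrees with the protocol's own statement about the effect after stopping, which MAR does not.

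**Conclusion.** The concern holds. For drug discontinuation, the planned treatment-regimen analysis will essentially reproduce the efficacy estimand and overstate the treatment-regimen effect. At 5% to 10% discontinuation the overstatement is roughly 1 to 4 points on the log-scale analysis, from half to full loss of effect by Week 12. The figures assume the plan's 60% on-drug reduction in every dose arm, an unchanged placebo arm, and a discontinuation rate and offset speed that the documents do not give; the 10% is a dropout figure used as a proxy. A few stops close to Week 12 may supply usable values, and whether the SAP 4.1 exclusion of off-schedule ED data reaches ED Lp(a) is arguable because Lp(a) is scheduled at that visit. Neither changes the conclusion. Superiority and power at the planned effect are unaffected; the size and interpretation of a secondary estimate are. It should be fixed.

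**What to change.** Amend SAP 4.1.2.2 before unblinding:

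- State the imputation for this estimand explicitly. For participants off drug with a missing Week 12 value, use placebo-based or return-to-baseline (washout) multiple imputation.
- Keep MAR for participants still on drug when the value went missing.
- Say whether an ED Lp(a) value inside the Week 12 window counts as the Week 12 value.
- Keep the tipping-point analysis as a sensitivity analysis.

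The Visit 801 Lp(a) values, already planned, can be used to judge whether the assumed return is reasonable.

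The cost is SAP wording and one imputation step, with no new data collection. The reported treatment-regimen effect will be slightly smaller, and possibly conservative for participants who stop late with only partial washout.

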4.1.2.3. Analysis method for safety

Unless specified otherwise, safety assessments will be guided by an estimand comparing safety of LY3473329 doses with placebo irrespective of adherence to intervention or initiation of Lp(a) modifying medications. Thus, safety analyses will be conducted using the SS (Section 3).

While considering treatment-emergent abnormal safety laboratory values and vital signs, the baseline observation period starts from the screening visit and ends prior to the first dose of study

intervention, wherein all scheduled and unscheduled measurements will be included. Baseline for the corresponding safety analysis will be the maximum/minimum (i.e., the most extreme/abnormal) from all these measurements during the baseline period. For postbaseline measurements, all scheduled and unscheduled measurements in the analysis period will be included. Table EKBC.4.2 the definition of baseline, postbaseline, and patient population for different safety endpoints.

4.2. Participant Dispositions

A listing and summary of study disposition for all randomized participants will be provided at the final database lock. Frequency counts and percentages of all participants screened, randomized, and receiving at least 1 dose of study drug will be presented by treatment groups. A listing and summary of randomized participants not receiving study drug will be provided. All participants who discontinue the study and/or study drug will be identified, and the extent of their participation in the study will be reported. If known, a reason for their discontinuation will be given. The primary reasons for discontinuation will be listed and summarized by treatment groups. Kaplan-Meier plots of time to study discontinuation, study treatment discontinuation, and study treatment discontinuation due to adverse event (AE) will be provided based on the all randomized population. Time-to-event analyses of study discontinuation, study treatment discontinuation, and study treatment discontinuation due to AE may be conducted.

Details about participant dispositions are included in the appendices: the demographic and baseline characteristics (Appendix 1, Section 6.1), historical illnesses and preexisting conditions (Appendix 2, Section 6.2), treatment compliance (Appendix 3, Section 6.3), concomitant medications (Appendix 4, Section 6.4), and important protocol deviations (Appendix 5, Section 6.5).

4.3. Primary Endpoint Analysis

The primary objective of the study is to demonstrate that LY3473329 10 mg, 60 mg, or 240 mg are superior to placebo with respect to percentage change from baseline in Lp(a) at Week 12.

4.3.1. **Definition of endpoint(s)**

The primary efficacy measure is percentage change from baseline in Lp(a) at Week 12, where baseline is defined as in Section 4.1.1.

4.3.2. Main analytical approach

The analytical approaches are specified for the efficacy estimand in Section 4.1.2.1 (MMRM) and for the treatment regimen estimand in Section 4.1.2.2 (ANCOVA). The primary efficacy measure will be log-transformed prior to statistical analyses.

For each estimand, LY3473329 will be declared superior to placebo in controlling Lp(a) if the p-value is less than 0.05 for both the analysis conducted with the apo(a) assay data and the analysis conducted with the intact Lp(a) assay data.

